8.5 Analyses prior to End of Scheduled Follow-up Visits

Any analyses conducted prior to the end of the scheduled follow-up visits should not compromise the integrity of the trial in terms of participant retention or safety or immunogenicity endpoint assessments. In particular, early unblinded analyses by treatment assignment require careful consideration and should be made available on a need to know basis only.

8.5.1 Safety

During the course of the trial, unblinded analyses of safety data will be prepared approximately every 4 months during the main study for review by the SMB. Ad hoc safety reports may also be prepared for SMB review at the request of the HVTN 124 PSRT. The HVTN leadership must approve any other requests for unblinded safety data prior to the end of the scheduled follow-up visits.

8.5.2 Immunogenicity

An unblinded statistical analysis by treatment assignment of a primary immunogenicity endpoint may be performed when all participants have completed the corresponding primary immunogenicity visit and data are available for analysis from at least 80% of these participants. Similarly, an unblinded statistical analysis by treatment assignment of a secondary or exploratory immunogenicity endpoint may be performed when all participants have completed the corresponding immunogenicity visit and data are available for analysis from at least 80% of these participants. However, such analyses for a secondary or exploratory immunogenicity endpoint will only take place after at least one of the primary immunogenicity endpoints of the same class (humoral, cell-mediated, innate or mucosal) or, if no primary endpoint of the same class, at least one of the primary immunogenicity endpoints reaches the aforementioned threshold. The Laboratory Program will review the analysis report prior to distribution to the protocol chairs,

DAIDS, vaccine developer, and other key HVTN members and investigators. Distribution of reports will be limited to those with a need to know for the purpose of informing future trial-related decisions. The HVTN leadership must approve any other requests for HVTN immunogenicity analyses prior to the end of the scheduled follow-up visits.

9 SAFETY TABLES AND FIGURES

9.1 List of Tables

SMB reports and Safety FSRs include the following tables.

- Enrollment Report
- Demographics and Vaccination Frequencies
- Overall Protocol Status
- Maximum Local and Systemic Reactogenicity Summaries
- Adverse Experiences by Body System and Severity – By Decreasing Frequency
- Adverse Experiences by Preferred Term and Severity – By Decreasing Frequency – Includes Severe, Life-threatening or Fatal Events Only
- Adverse Experiences by Preferred Term and Severity – By Decreasing Frequency – Includes Events of All Severities
- Adverse Experiences by Preferred Term and Severity – By Decreasing Frequency – Includes Related Events Only
- Adverse Experiences by Preferred Term and Relationship to Study Product – By Decreasing Frequency – Includes Events of Any Relationship
- Expedited Adverse Experiences (EAEs) Reported to the Regulatory Support Center (RSC)
- Pregnancy Listing
- AEs of Special Interest (AESI)
- Summary of Adherence to Pause Rules
- Summary of Immediate/Prompt PSRT AE Reviews

9.2 Participant Listings

The following listings of participant-level data are included in the SMB reports.

- Discontinuations
- Pregnancies
- Severe or Life-Threatening Local and Systemic Reactogenicities
- Moderate or Severe Erythema and Induration
- Expedited Adverse Experiences (EAEs)
- Adverse Experiences of Special Interest (AESIs)
- Severe, Life-Threatening, or Fatal Adverse Experiences
- Adverse Experiences with Relationship to Study Product (Grade 2 or higher)
- HIV Infection Results from Lab and Reported by Site
- Study Product Administration Errors

9.3 List of Graphs

- Maximum Local Reactogenicities
- Maximum Systemic Reactogenicities
- Boxplots for Alkaline Phosphatase, AST, ALT, Creatinine, WBC, Hemoglobin, Platelets, Lymphocyte Count, and Neutrophil Count.

10 IMMUNOGENICITY TABLES AND FIGURES, BY ASSAY

10.1 Binding Antibody Multiplex Assay (BAMA)

Serum HIV-1-specific IgA and IgG antibody binding responses will be measured at a 1:10 dilution for IgA and 1:50 dilution for IgG, respectively, against various antigens on a Bio-Plex instrument (Bio-Rad) using a standardized custom HIV-1 Luminex assay (Tomaras and Yates et al., J Virology 2008). The readout is background-subtracted mean fluorescence intensity (MFI), where background refers to a plate-specific background measure. Net MFI is MFI minus Blank, where 'Blank' refers to a sample-specific background measure.

BAMA testing will be performed on all participant serum samples collected from Part A, study Group 1 at visits 2 (Month 0) and 5 (Month 2.5, 2 weeks post the 2nd vaccination) and from Part B: study Groups 2 and 3 at visits 12 (Month 0) and 22 (Month 8.5, 2 weeks post the 5th last vaccination). Specimens from other timepoints as well as other HIV antigens and antibody isotypes may be assayed based on the results of the initial assay. If sufficient immunogenicity is observed for the primary analysis antigens, additional assays will be performed using the exploratory antigens.

The following table lists the antigens for the primary analysis.

Panel	Antigen	Clade	Isolate
Vaccine Recombinant Protein	gp120	A	IgG/IgA
	gp120	B	IgG/IgA
	gp120	C	IgG/IgA
	gp120	AE	IgG/IgA
gp120 Breadth Panel	51802_D11gp120.avi/293F	A1	IgG
	BORI_D11gp120.avi/293F	B	IgG
	TT31P.2792_D11gp120.avi/293F	B	IgG
	B.6249_D11gp120/293F	B	IgG
	A244_D11gp120_avi	CRF01-AE	IgG
	254088_D11gp120.avi/293F	CRF01-AE	IgG
	CNE20_D11gp120.avi/293F	CRF07-BC	IgG
	BJOX002_D11gp120.avi/293F	CRF07-BC	IgG
gp70 V1V2 Breadth Panel	gp70-191084_B7_V1V2	A	IgG
	gp70_B.CaseA_V1_V2	B	IgG
	gp70-RHPA4259.7V1V2	B	IgG
	gp70-62357.14_V1V2	B	IgG
	gp70-700010058_V1V2	B	IgG
	gp70-TT31P.2F10.2792_V1V2	B	IgG
	gp70-BF1266_431a_V1V2	C	IgG
	gp70-7060101641_V1V2	C	IgG
	gp70-96ZM61.01_V1V2	C	IgG
	gp70-0014282.42_V1V2	C	IgG
	gp70-CAP210.2.00.E_8_V1V2	C	IgG

	gp70-TV.21 V1V2	C	IgG
	gp70-Ce1086 B2 V1V2	C	IgG
	gp70-CM244.ec1 V1V2	CRF01 AE	IgG
	gp70-C2101.c01 V1V2	CRF01 AE	IgG
	gp70-BJOX002000.03.2 V1V2	CRF07-BC	IgG
Consensus gp140/gp120	Con S gp140 CFI	M	IgG/IgA
	Con 6 gp120/B	M	IgG/IgA
	1086_DCgp120.avi/293F	C	IgG/IgA
	gp41		IgG/IgA
	P24	B	IgG/IgA
	A1.con.env03 140 CF	A	IgG/IgA
	00MSA 4076 gp140	A	IgG/IgA

The following table lists the antigens for exploratory analysis if sufficient immunogenicity responses are observed (for Part B only).

Panel	Antigen	Clade	Isolate
Extended Clade C gp120 Panel	1394C9_G1.D11gp120.avi	C	IgG
	1428_D11gp120.avi/293F	C	IgG
	1641A7_D11gp120.avi/293F	C	IgG
	CAP210_D11gp120.avi/293F	C	IgG
	CAP45_D11gp120.avi/293F	C	IgG
	Ce0042_D11gp120.avi/293F	C	IgG
	CH505TF_D7gp120.avi/293F	C	IgG
	Du156_D11gp120.avi/293F	C	IgG
	96XM651.D11gp120.avi	C	IgG
	TV1c8_D11gp120.avi/293F	C	IgG
Extended Clade C V1V2 Panel	gp70-CAP45.2.00.G3 V1V2	C	IgG
	gp70-1294C9G1_V1V2	C	IgG
	gp70-1012.11.TC21.3257 V1V2	C	IgG
	gp70-1051.12.C22 V1V2	C	IgG
	gp70-Ce1176 V1V2	C	IgG
	gp70-Ce704010042_2ES V1V2	C	IgG
	gp70-ConcC V1V2	C	IgG
	gp70-DU156.12.V1V2	C	IgG

Several criteria are used to determine if data from an assay are acceptable and can be statistically analyzed. The blood draw date must be within the allowable visit window as determined by the protocol. Second, if the blank bead negative control exceeds 5,000 MFI, the sample will be repeated. If the repeat value exceeds 5,000 MFI, the sample will be excluded from analysis due to high background.

Samples from post-enrollment visits are declared to have a positive response if they meet three conditions:

1. The net MFI values \geq antigen-specific cutoff (based on the 95th percentile of the baseline net MFI values that are greater than/equal to 100 but less than 6,500). If the cutoff is greater than 5,000 net MFI, then the antigen will be excluded from analysis.
2. The net MFI values are greater than 3 times the baseline net MFI values.
3. The MFI values are greater than 3 times the baseline MFI values.

For each of gp120 breadth panel and gp70 V1V2 breadth panel, magnitude-breadth (MB) and AUC-MB will be calculated for each participant by isotype and post-vaccination timepoint.

Contingent upon these results, samples may be titrated to calculate antibody titers (EC50/AUC), in which case geometric mean titers will be compared.

The treatment arm of receiving 2 protein/GLA-SE vaccines is labelled as T1, the treatment arm of receiving 3 DNA prime vaccinations and 2 DNA+Protein/GLA-SE boost vaccinations in Group 2 is labelled as T2, and the treatment arm of receiving 5 DNA+Protein/GLA-SE vaccinations in Group 3 is labelled as T3. The placebo arm in Part A is labelled as P_A. The placebos in Groups 2 and 3 in Part B are pooled and the treatment arm is labelled as P.

The binding antibody response rates will be compared between treatment arms within each timepoint using Barnard exact test. The response magnitudes, AUC-MB will be compared between treatment arms within each timepoint using Wilcoxon rank sum test. The comparisons of response rates between timepoints within each of treatment arms will be performed using McNemar's test if binding antibody responses will be measured at multiple timepoints.

Similarly, the comparisons of binding antibody response magnitudes, AUC-MB between timepoints within each of treatment arms will be compared using Wilcoxon signed rank test.

If antibody titers (EC50/AUC) data are available, two sample t-test will be used to compare log-titers (EC50/AUC) between two treatment arms within each timepoint and paired t-test will be used to compare log-titers between timepoints within each of treatment arms.

The following tables and figures are generated separately for Part A and Part B unless are specified otherwise.

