The PDPHV-201401 protocol differs from the above approaches by using gp120 from 4 different major subtypes of HIV-1, to expand the breadth of the immune responses. A DNA prime is used instead of a viral vector prime, to avoid vector-specific immune responses and focus immune responses against the Env immunogen inserts.

The vaccine regimens to be tested are multigenic, polyvalent, and heterologous – three important characteristics to use in HIV vaccine strategy. As it is unlikely that antigens from any one gene would be sufficient for an effective HIV regimen, the vaccine regimens include both Env and Gag for their respective abilities to elicit antibody and T cell responses. For a frequently mutating virus with multiple subtypes such as HIV-1, it is important to have multiple variants of a protective immunogen (envelope protein, Env) to produce a polyvalent formulation. This vaccine regimen includes four Env antigens from subtypes A, B, C, and A/E. Notably, IgG to subtype A, B, C and CRF01_AE V1V2-scaffold antigens were also identified as inverse correlates of risk in the RV144 trial. Additional correlates were IgG to V3 CRF01_AE and plasma levels of antibody-dependent cell-mediated cytotoxicity (ADCC) activity against Env V2, in the setting of low Env-specific binding IgA (19, 21, 24). This polyvalent vaccine regimen has the potential to elicit those responses. It has been demonstrated in a previous phase 1 trial (DP6-001) (25) that the sequential administration of two types of vaccines (DNA and protein) delivering the same subunit gp120 antigens was more effective than either type of vaccine alone. Therefore, HVTN 124 will compare the relative immunogenicity between sequential administration and co-administration of the DNA vaccine and the matching recombinant gp120 (A, B, C, A/E) proteins in GLA-SE adjuvant. The potential advantages of co-administration are earlier induction of antibody, which if effective, would lead to earlier protection, and higher cumulative doses of both DNA and protein vaccine products, in comparison with the sequential DNA–protein immunization approach. An important objective is to determine which approach will achieve the highest response rate, magnitude, and durability of antibody responses, and to characterize any qualitative differences in immune responses to the two regimens.

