6.1 Accrual and sample size calculations

Recruitment will target enrolling 60 healthy, HIV-uninfected adult participants.

The protocol is composed of two parts, Part A and Part B. Part A will assess the safety of recombinant gp120 (A, B, C, A/E) protein/GLA-SE adjuvant. Part B will evaluate the safety and immunogenicity of DNA prime and protein/adjuvant boost or DNA and protein/adjuvant co-administered. Part A will proceed prior to Part B. In Part A, 12 participants will be enrolled and randomized to receive either the protein or a placebo with a 5:1 ratio. In Part B, 48 participants will be enrolled into Group 2 and Group 3 with a 1:1 ratio. Within each group, the participants will be randomized to receive either the vaccine (DNA prime and protein/adjuvant boost in Group 2 and DNA+protein/adjuvant co-administered in Group 3) or a placebo with a vaccine:placebo ratio of 7:1. Therefore, in Group 2, 21 participants will receive the DNA prime and protein/adjuvant boost and 3 will receive the placebo; in Group 3, 21 participants will receive the DNA and protein/adjuvant co-administered and 3 participants will receive the placebo.

To ensure that both men and women will be adequately represented in the trial, the trial will attempt to enroll approximately 40% to 60% of each sex assigned at birth overall in each Part. Hence, at least 5 participants in Part A and 19 participants in Part B of each sex will be enrolled.

Since enrollment is concurrent with receiving the first study vaccination, all participants will provide some safety data. However, for immunogenicity analyses, it is possible that data may be missing for various reasons, such as participants terminating from the study early, problems in shipping specimens, or low cell viability of processed peripheral blood mononuclear cells (PBMCs). Immunogenicity data from nine phase 1 and one phase 2a HVTN vaccine trials, which began enrolling after June 2005 (data as of September 2014), indicate that 10% is a reasonable estimate for the rate of missing data at early timepoints (≤ 6 months) and 15% for later timepoints (> 6 months). For this reason, the sample size calculations in Section 6.1.1 account for 15% enrolled participants having missing data for the primary immunogenicity endpoint.

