8.4 Immunogenicity Analysis

8.4.1 General approach

For the statistical analysis of immunogenicity endpoints, data from enrolled participants will be used according to the initial randomization assignment regardless of how many injections they received. Additional analyses may be performed, limited to participants who received all scheduled injections per protocol. Assay results that are unreliable, from specimens collected

outside of the visit window, or from HIV-infected participants post infection are excluded. Since the exact date of HIV infection is unknown, any assay data from blood draws 4 weeks prior to an infected participant's last seronegative sample and thereafter may be excluded. If an HIV-infected participant does not have a seronegative sample post enrollment, then all data from that participant may be excluded from the analysis.

Discrete categorical assay endpoints (eg, response rates) will be analyzed by tabulating the frequency of positive response for each assay by antigen and treatment arm at each timepoint for which an assessment is performed. Crude response rates will be presented with their corresponding 95% confidence interval estimates calculated using the score test method (52). Because of the small numbers of control participants in each group, no adjustment will be made to the vaccine arm estimates for the false positive rates in the control arms. Barnard or Fisher's exact tests, as specified in the SAP, will be used to compare the response rates of any 2 vaccine arms, with a significant difference declared if the 2-sided p-value is ≤ 0.05 . In general Barnard's is preferred since under most circumstances it is more powerful than Fisher's (54).

In addition to response rate estimates for each timepoint, the probability of observing at least 1 positive response by a given timepoint and the probability of observing more than 1 positive response by a given timepoint will be estimated, with corresponding confidence intervals, for each vaccine arm using maximum likelihood-based methods (55).

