10.1.1 List of Tables

- The binding antibody positive response rates by isotype, antigen, visit and treatment arm
- Summary statistics for magnitudes among the positive responders by isotype, antigen, visit and treatment arm
- Summary statistics for AUC-MB by isotype, breadth panel, visit, and treatment arm
- The comparisons of response rates between T2 and T3 by isotype, antigen, and visit
- The comparisons of response magnitudes between T2 and T3 by isotype, antigen, and visit
- Lists of the positive responders and the magnitudes for those participants
- The comparisons of AUC-MB between T2 and T3 by isotype, breadth panel, and visit
- Geometric mean and 95% CI of titers (EC50/AUC) by isotype, antigen, visit, and treatment arm. 95% CI will be calculated based on a normal approximation for log-transformed titers.
- The comparisons of titers (EC50/AUC) between T2 and T3 by isotype, antigen and visit.
- The comparisons of AUC-MB of titers (EC50/AUC) between T2 and T3 by isotype, breadth panel, and visit

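### The BAMA cutoff is a 95th percentile over only those baselines from 100 to below 6,500 net MFI, so it rests on one or two values when few are in range and does not exist when none is

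*SAP*

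**What the plan says.** SAP 10.1 gives the call rule: "Samples from post-enrollment visits are declared to have a positive response if they meet three conditions". The first condition is that net MFI reaches an antigen-specific cutoff, "based on the 95th percentile of the baseline net MFI values that are greater than/equal to 100 but less than 6,500". The other two require more than a 3-fold rise over the participant's own baseline, in net MFI and in MFI.

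The only contingency for the cutoff is at the high end: "If the cutoff is greater than 5,000 net MFI, then the antigen will be excluded from analysis". SAP 10.1 gives no minimum number of in-range baselines, no default when none is in range, no percentile definition, and no statement of whether Part A and Part B baselines are pooled. Protocol 6.4.4.8 defers the positivity definition to the SAP, so it supplies no fallback.

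The calls feed the response-rate tables and the magnitudes among responders in SAP 10.1.1, including "The comparisons of response rates between T2 and T3 by isotype, antigen, and visit". Protocol 4.1 states: "An important objective is to determine which approach will achieve the highest response rate, magnitude, and durability of antibody responses".

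**The concern.** As written, 100 is an entry rule for the percentile and not a floor under the cutoff. Baselines below 100 are the best evidence that an antigen has low background, and they are dropped before the percentile is taken. The lower the background, the fewer values remain and the closer the percentile moves to their maximum. One or two participants can then set the cutoff for everyone. If no baseline reaches 100, condition 1 cannot be evaluated. Because all three conditions are required, no response can then be called.

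At stake are the level and stability of the IgG and IgA response rates and the responder-only magnitudes for low-background antigens. Someone would also have to devise a cutoff after seeing the baseline data.

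**Working it through.** The plan states no figure that depends on this cutoff, so there is none to reproduce.

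**Inputs.** Protocol 6.1: "In Part A, 12 participants will be enrolled and randomized" and "In Part B, 48 participants will be enrolled into Group 2 and Group 3 with a 1:1 ratio". So there are at most 12 baselines (Part A), 48 (Part B) or 60 (pooled). The primary antigen table in SAP 10.1 lists 35 IgG and 11 IgA pairs, 46 in all. The share f of baselines in range is not given and is assumed throughout.

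**1. Which values set the cutoff.** Under linear interpolation, the 95th percentile of m values lies 0.05(m − 1) places below the maximum.
- m = 3: 0.10 places, so 90% of the weight is on the largest value.
- m = 6: 0.25 places, 75% on the largest.
- m = 12: 0.55 places, 45% on the largest.
- m = 21: 1.0 place, exactly the second largest.
- m = 60: 2.95 places, between the 3rd and 4th largest.

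So up to m = 21 only the top two values matter. Under the SAS default definition this extends to m = 39. With 48 baselines, the probability of 20 or fewer in range is above 0.999 at f = 10% or 20%, 0.97 at 30% and 0.16 at 50%.

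The percentile definition matters too. Take ten in-range values, nine between 110 and 400 and one at 5,500. The SAS default gives 5,500, so the antigen is excluded. The R default gives 3,205, so it is kept. SAP 8 allows either package.

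**2. Direction.** The comparator is max(100, 95th percentile of all baselines below 6,500). Restoring the values under 100 only adds low values. This raises m and moves the percentile further below the same maximum. Every in-range value is at least 100. The cutoff as written is therefore never below the comparator.

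**3. No cutoff.** P(none in range) = (1 − f)^n.
- n = 60: 0.95^60 = 4.6%; 0.90^60 = 0.2%.
- n = 48: 0.95^48 = 8.5%; 0.90^48 = 0.6%.
- n = 12: 0.95^12 = 54%; 0.90^12 = 28%.

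If all 46 pairs had f = 5% and baselines were pooled, 46 × 0.0461 = 2.1 pairs would be expected to lack a cutoff. At f = 10% it is 46 × 0.0018 = 0.08.

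**4. Size of the shift (assumed).** Simulation of 6,000 antigens per setting, with log10-normal baselines and P(at least 100) = f. Median cutoffs at n = 60, SD 0.5:

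| f | as written | comparator | ratio | ratio at SD 0.7 |
|---|---|---|---|---|
| 5% | 207 | 100 | 2.07 | 2.76 |
| 10% | 292 | 138 | 2.12 | 2.88 |
| 20% | 438 | 229 | 1.91 | 2.44 |
| 50% | 824 | 601 | 1.37 | 1.51 |
| 80% | 1,737 | 1,557 | 1.12 | 1.10 |

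Over n = 48–60 the ratio is 1.8–2.9 at f = 5–20%. The cutoff also varies more between antigens: at f = 5% (n = 60, SD 0.5) its 10th–90th percentiles are 126–411 as written and 100–134 for the comparator.

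**5. Effect on calls (assumed).** Here the post-vaccination value is a fixed multiple of the participant's own baseline, visit noise is SD 0.15 log10, and MFI and net MFI are treated as equal. Only antigens with a cutoff are counted. For n = 60, f = 5–20%, as written v comparator:
- SD 0.5: 10-fold 39–45% v 61–66%; 30-fold 72–78% v 89–91%; 100-fold 94–96% v 99%.
- SD 0.7: 10-fold 21–25% v 39–45%; 30-fold 43–49% v 65–71%; 100-fold 69–75% v 87–90%.
- f = 80%, SD 0.5: 10-fold 64% v 67%; 30-fold 90% v 92%.

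These folds start low. At f = 5% the assumed median baseline is 10^(2 − 1.645 × 0.5) = 15 net MFI for SD 0.5 and about 7 for SD 0.7. A 10-fold rise from 15 reaches only about 150, and a 30-fold rise from 7 about 210.

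**The case against.** The strongest reply is that the SAP states a deterministic rule, that only the empty case is a true gap, and that the rest is a preference for sensitivity over specificity. The documents promise no 5% exceedance rate over all baselines, so the ratios compare the rule with a chosen alternative. The words before the percentile are also loose, and 100 may have been meant as a floor. Part of this stands: no promised error rate is broken. But a cutoff that rests on fewer values as background falls is a weakness in its own right, and if a floor was meant, the text still needs changing to say so.

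The call-rate losses depend on the fixed-multiple model. If vaccination instead adds MFI independently of baseline, a median gain of 5,000 net MFI (assumed log10 SD 0.3, n = 60, f = 5–20%) gives 97.5–100% called as written and 99.5–100% with the comparator. Gaps remain at gains of 500–1,000. This stands: the loss is confined to weak and moderate responses. Protocol 4.8.1 reports high anti-gp120 titres with the predecessor regimen, though in another assay.

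A reader might infer three stronger things that the documents do not support.
- **Bias between T2 and T3.** Both arms face the same cutoff.
- **Damage to secondary endpoint 1.** That endpoint is magnitude and breadth. The SAP does not make AUC-MB depend on the positivity call, so it changes only if an antigen is excluded.
- **A cutoff too high against any alternative.** Compared with the percentile of all baselines, including those at or above 6,500, it can go either way. With one such value among 48 or 60, it is lower if up to 18 baselines are under 100 and higher if 20 or more are.

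**Conclusion.** The point holds as a should-fix matter, with medium confidence. Three parts follow from the SAP text and need no assumed MFI values: the cutoff depends on the largest one or two values when 21 or fewer baselines are in range; it has no value when none is; and it is never below the floored percentile of all baselines below 6,500.

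How often this matters is not known. The shift and the call-rate losses rest on the assumed share in range and log-normal baselines, and the losses also on the fixed-multiple response model. They are material when 5–20% of baselines are in range and small when most are. The expectation of 2.1 pairs without a cutoff needs every pair at 5% and all 60 baselines pooled, and should not be read as a forecast.

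**What to change.** Reword condition 1 so that the cutoff is *the larger of 100 net MFI and the 95th percentile (linear interpolation) of all baseline net MFI values below 6,500 for that antigen and isotype*. Keep conditions 2 and 3 and the 5,000 exclusion.

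Name the baseline set as well. Pooling all participants would fit badly with Part A, which runs first, is unblinded independently and has separate BAMA outputs: its calls would have to wait for Part B baselines or change afterwards. One workable choice is Part A cutoffs from Part A baselines, and Part B cutoffs from Part B baselines (or all baselines assayed by then), without re-calling Part A. A Part A cutoff from at most 12 baselines would still rest on its top one or two values, but it would exist and be at least 100 whenever any baseline is below 6,500.

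The work is a short SAP edit and a small code change, before BAMA data are analysed. The statistical cost is a less strict condition 1. At f = 5–20% and n = 48–60, background exceedance of that condition alone goes from 1.4–2.5% to 4.3–6.7%. With all three conditions and no true rise, false calls go from 0.04–0.09% to 0.11–0.20% (within-person SD 0.15 log10 per visit), or from 0.3–0.7% to 0.8–1.6% (SD 0.25). Over 8 placebo recipients × 46 pairs = 368 calls, the SD 0.25 case is about 1–3 false positives as written and 3–6 after the change. SAP 8.4.1 says "no adjustment will be made to the vaccine arm estimates for the false positive rates in the control arms", so this should be acknowledged when the rule is adopted.
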